**[name]**

**ACTG Network Coordinating Center**

**Social & Scientific Systems, Inc., A DLH Holdings Company**

**[name]  
[name] [name]  
[contact]  
E-mail: [[contact]](mailto:[contact])**

Laboratory Data Manager  
[name]  
Frontier Science and Technology Research Foundation  
[name]  
[name]  
[contact]  
E-mail: [[contact]](mailto:[contact])

**[name]  
Frontier Science and Technology Research Foundation  
[name]  
[name]  
[contact]  
E-mail: [[contact]](mailto:[contact])**

2. The following clarification applies to the third sentence of the second paragraph in section 10.4, Sample Size and Accrual. In that sentence, a typographical error occurs; this sentence should read as shown below, for consistency with eligibility criteria 4.2.10 and 4.2.11.

**“Arm B participants who discontinue the study prior to Day 14 without sufficient virology data (as judged by the CST), or beginning with Version 4.0 of the protocol, who have an entry plasma HIV-1 RNA <50 <5000 copies/mL, will be replaced to ensure enough efficacy data are available for dose de-escalation evaluation.”**

These clarifications will be included in the next version of the A5377 protocol if it is amended at a future date.

4.0	Changes made to accommodate modifications in PK analysis as the result of never opening Arm B Cohort 7 (10 mg/kg) and limited enrollment in Arm B Cohorts 5 (1 mg/kg) and 8 (30 mg/kg). Changes are bolded.	October 23, 2023

1 Introduction

1.1 Purpose

This Primary Statistical Analysis Plan (SAP) describes the primary and secondary outcome measures of the ACTG A5377 study that will be included in the primary manuscript(s), and which address, at a minimum, the primary and secondary objectives of the study. The Primary SAP outlines the general statistical approaches that will be used in the analysis of the study. It has been developed to facilitate discussion of the statistical analysis components among the study team, and to provide agreement between the study team and statisticians regarding the statistical analyses to be performed and presented in the primary analysis report. It also describes the results for the primary and secondary outcome measures that will be posted on ClinicalTrials.gov. This document corresponds to A5377 Protocol Version 4.0.

The SAP outlines the outcome measures and statistical principles for all parts of the primary analysis report. These may be modified as new information becomes available or to reflect recommendations of the Safety Monitoring Committee (SMC).

Detailed outlines of tables, listings, and figures that will be included in the primary analysis report are included in the Analysis Implementation Plan (AIP). The AIP will also provide specific coding details, data sources, and validation requirements.

1.2 Version History

In Version 1.1, [REDACTED] reviewed the SAP in light of LOA #1. No substantive changes were required.

In Version 2.0, changes were made to accommodate Version 3.0 of the protocol. These changes include the addition of a subcutaneous injection arm (Arm C, Cohorts 10 and 11) and dose de-escalation design in Arm B. A COVID-19 specific appendix was also added. Changes from Version 1.0 are shown in red.

In Version 2.1, [REDACTED] reviewed the SAP in light of Version 3.0, LOA #2. No substantive changes were required.

In Version 3.0, [REDACTED] reviewed the SAP in light of Version 4.0 of the protocol. No substantive changes were required but minor modifications were made throughout (and are bolded). The visit window section (4.1) was clarified and the corresponding tables (Table 1 and 2) were removed and added to the primary AIP where they were further edited for clarity (and to capture instances where multiple samples were obtained during a single visit [e.g., intensive PK and HIV-1 RNA]).

In Version 4.0, the SAP was reviewed in light of the closing of the study without opening Arm B Cohort 7 (10 mg/kg) and limited enrollment into Arm B Cohorts 5 (1 mg/kg) and 8 (30 mg/kg). Changes were made to the planned PK analyses (primary and secondary) as well as some secondary efficacy analyses. Changes are bold.

2 Study Overview

2.1 Study Design

A5377 is a phase 1, first-in-human study of SAR441236. It will include three arms with multiple cohorts in each arm.

2.2 Regimen

Double-blind randomization in Arms A and C will be 2:1 SAR441236:placebo. Arm B participants will all receive open-label SAR441236.

Arm A (Treated, virologically suppressed)

- Cohort 1: 1 mg/kg of SAR441236 or saline placebo administered as a single intravenous (IV) infusion. Cohort 1 enrollment was completed under Protocol Version 2.0.
- Cohort 2: 3 mg/kg of SAR441236 or saline placebo administered as a single IV infusion. Cohort 2 enrollment was completed under Protocol Version 2.0.
- Cohort 3: 10 mg/kg of SAR441236 or saline placebo administered as a single IV infusion. Cohort 3 enrollment **was completed** under Protocol Version 2.0.
- Cohort 4: 30 mg/kg of SAR441236 or saline placebo administered as an IV infusion every 12 weeks for a total of four infusions. Cohort 4 enrollment **began** under Protocol Version 2.0 **and completed under Protocol Version 3.0**.

Arm B (HIV viremic)

- Cohort 5: 1 mg/kg of SAR441236 administered as a single IV infusion. **Cohort 5 enrollment began under Protocol Version 2.0 and was closed with Protocol Version 3.0.**
- Cohort 7: 10 mg/kg of SAR441236 administered as a single IV infusion. **Cohort 7 never opened to enrollment.**
- Cohort 8: 30 mg/kg of SAR441236 administered as a single IV infusion. **Cohort 8 enrollment began under Protocol Version 3.0. No additional participants enrolled under Protocol Version 4.0.**

In protocol Version 4.0, participants in Arm B will initiate or re-initiate combination non-study-provided ART on Day 14.

Arm C (ART-treated, virologically suppressed)

- Cohort 10: 0.3 mg/kg of SAR441236 or saline placebo administered once via a single subcutaneous (SC) injection on a single day.
- Cohort 11: 1 mg/kg of SAR441236 or saline placebo administered once via single or multiple SC injections on a single day.

Figure 1: Schema Arm A

[figure not shown]

Figure 2: Schema Arm B

[figure not shown]
[figure not shown]

Figure 3. Schema Arm C

2.3 Hypotheses

1. Infusion of SAR441236 is safe and well tolerated at the proposed doses.
2. The pharmacokinetics (PK) of SAR441236 after infusion of a single dose is similar in viremic and virologically suppressed participants with HIV.
3. SAR441236 has dose-dependent anti-HIV-1 activity in viremic participants with HIV.
4. Subcutaneous injection of SAR441236 is safe and well tolerated at the proposed doses.

2.4 Study Objectives

This Primary SAP addresses the primary and secondary objectives listed in the study protocol. The primary PK outcome estimates will be generated outside of the SDAC by the protocol pharmacologist and their estimation procedure and analyses will be defined in a separate document. The remaining study objectives listed in the protocol will be addressed in subsequent analysis plans.

2.4.1 Primary Objectives

1. To evaluate the safety and tolerability of single doses of SAR441236 in virologically suppressed participants with HIV receiving ART (Arm A, Cohorts 1-3, and Arm C, Cohorts 10 and 11) and in viremic participants with HIV (Arm B), and of multiple doses in virologically suppressed participants with HIV who are receiving ART (Arm A, Cohort 4).
2. To evaluate the PK of single doses of SAR441236 in virologically suppressed participants with HIV receiving ART (Arm A, Cohorts 1-3, and Arm C, Cohorts 10 and 11), and in viremic participants with HIV (Arm B), and of multiple doses in virologically suppressed participants with HIV who are receiving ART (Arm A, Cohort 4).

3. To evaluate the antiviral activity of a single dose of SAR441235 in viremic participants with HIV at Day 7 after the infusion (Arm B).

2.4.2 Secondary Objectives

1. To evaluate the dynamics of plasma HIV-1 RNA decay in viremic participants receiving SAR441236 (Arm B).
2. To evaluate the antiviral activity of a single dose of SAR441236 at Day 14 and Day 28 and the maximum antiviral activity of a single dose of SAR441236 from baseline to Day 28 in viremic participants (Arm B).
3. To evaluate if anti-SAR441236 antibodies are induced after single or multiple doses.
4. To evaluate the effects of single and multiple doses of SAR441236 on CD4+ T-cell counts.
5. To establish concentration (or dose)-response relationships between SAR441236 exposure and changes in plasma HIV-1 RNA from entry to week 4 (or viral load nadir) in Arm B.

2.5 Overview of Sample Size Considerations

The total sample size of this study is **53-65** evaluable participants (**39-51** active-treated participants and 14 placebo participants). In Arms A and C, the proposed sample size provides a reasonably high probability of dose escalation when the true event rates are in fact acceptable, as well as providing low probability of dose escalation when the true event rates are unacceptable. In Arm B, the proposed sample sizes and dose de-escalation scheme (described in Protocol Section 10.4.2) provide a reasonably high probability of dose de-escalation when the true response rate (i.e., HIV-1 RNA reduction of at least $1.0 \log_{10}$ copies/mL from baseline by Day 14) for a given dose cohort is high.

For the primary outcome measure of efficacy in Arm B, the study has 80% power to detect a drop of $1.7 \log_{10}$ copies/mL in plasma HIV-1 RNA in each cohort with $N = 6$.

In all cohorts, participants who do not receive study treatment or who receive less than 90% of their first or only intended infusion or SC injection dose will be replaced. Arm A or Arm C participants who discontinue the study prior to Day 14 without having met the primary safety endpoint **OR. Beginning with Version 4.0 of the protocol, have an entry plasma HIV-1 RNA <5000 copies/mL**, will be replaced to ensure enough **efficacy** data are available for dose **de**-escalation evaluation. The CST may decide on additional replacements if primary endpoints cannot be adequately assessed due to missing data or incorrect infusion procedure. Participants who initiate the infusion or SC injection but receive less than 90% of their first or only intended dose will be encouraged to remain on study and complete all study follow-up.

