For the primary efficacy analyses for Arm B cohorts, reduction in plasma HIV-1 RNA (\log_{10} copies/mL) from baseline to Day 7 will be summarized, both in a combined cohort and in each cohort separately. The comparison between pre- and post-treatment will be carried out using a paired t-test with 2-sided 95% confidence interval for the combined cohort, and a Wilcoxon signed rank test for each cohort separately. The analyses will use the Efficacy population defined in Section 4.1.1. **Sensitivity analysis will be carried out using a Wilcoxon signed rank test for the combined cohort.**

Sensitivity analysis including the Safety population as defined in Section 4.1.1 will be conducted.

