4.2.2 Analysis of Secondary Outcomes

- **Plasma HIV-1 RNA (\log_{10} copies/mL) at baseline and post-infusion for treatment-naïve, viremic participants with HIV (Arm B cohorts)**

Longitudinal participant-specific plots for antiviral activity before initiation of ART will be presented for each participant in Arm B. **Given the little evidence of viral decay in Cohort 5 and the limited sample size in Cohort 8 (n=2), the planned modelling for viral decay will not be conducted.**

- **Change in plasma HIV-1 RNA (\log_{10} copies/mL) from baseline (defined as the last measurement taken prior to treatment initiation) to Day 7 and Day 14 of monotherapy, and maximum reduction during 14 days of monotherapy for treatment-naïve, viremic participants with HIV (Arm B cohorts)**

Similar analyses described in section 4.2.1 for the primary efficacy endpoint at Day 7 will be conducted for the Day 14 results. Summary statistics will be provided for the maximum reduction of each participant by dose cohort during monotherapy of SAR441236 (post-infusion and before ART initiation). **Protocol Version 4.0 considers the maximum reduction during 14 days of monotherapy because the timing for ART initiation/re-initiation was changed from “by 28 days” (Version 3.0 or earlier) to “at 14 days” for Arm B participants. However, since no participants enrolled under Version 4.0, we consider maximum reduction occurring in up to 28 days of monotherapy for Arm B participants.**

- **Attributions of anti-SAR441236 antibodies in all cohorts.**

The ADA status of participants exposed to anti-SAR441236 antibodies will be tabulated by scheduled visit day/week. Details of participants who developed anti-SAR441236 antibodies will be provided.

- **Change in CD4⁺ T-cell counts (cells/mm³) from baseline to week 12 following single dose of SAR441236 for all cohorts and the change in CD4⁺ T-cell counts (cells/mm³) from baseline to week 12 following each infusion for Cohort 4.**

Longitudinal participant-specific plots and numerical summaries for change from baseline in CD4⁺ T-cell counts (cells/mm³) will be presented by cohort.

- **Pharmacokinetic parameters of SAR441236 following each infusion.**

Descriptive numerical summaries of the following PK parameters (protocol section 11.3) by dose cohort will be presented:

Single dose:

- Maximum concentration (C_{max})
- Time of maximum concentration (T_{max})
- Dose-normalized maximum concentration
- Terminal half-life

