- Analysis windows have been widened to capture as much information as possible. For participants who received their infusion shortly before the pause, they were directed to the Single Dose Arm A SOE (Table 6.1-1 in Protocol Version 2.0) after they had reached Week 4 to reduce site burden. This will cause slight differences in visit schedules across Cohort 4 participants. However, the majority of these were virtual (no lab data collected) so the need to align lab results (e.g., CD4+ T-cell counts) will be negligible.

Arm B Single Dose Cohort (5) Considerations

- Four participants were on-study in Cohort 5 during the COVID-19 pause. One participant had completed the specified 24-week follow-up and was off study before the pause. All participants had reached Day 28 and initiated ART by the end of February 2020.
- **IMPACT: MODERATE**
 - There is no impact to the primary efficacy outcome (i.e., all participants had reached Day 28 before the COVID-19 pause) nor to any secondary outcome involving HIV-1 RNA.
 - The primary PK endpoint has the potential to be affected as some Week 12 visits were conducted virtually (and thus no labs were collected). The A5377 team pharmacologist will make the appropriate accommodations in the calculation of the PK parameters and document them in the PK analysis plan.
 - Analysis windows have been widened to capture as much information as possible. The Week 24 visit window will be further expanded to capture in-person visits for all participants.
 - Note: Per Protocol Version 3.0 this Cohort 5 will be closed (although it did not enroll 6 participants).

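### SAP Section 2.5 still gives 53-65 participants and 80% power per Arm B cohort at N = 6, but no Arm B cohort reached 6 and the per-cohort tests kept in 4.2.1 cannot reach two-sided 0.05

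*SAP*

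**What the plan says.** SAP Section 2.5 opens with "The total sample size of this study is" 53-65 and breaks this down as "evaluable participants (39-51 active-treated participants and 14 placebo participants". On power it says "For the primary outcome measure of efficacy in Arm B, the study has 80% power to detect a drop of" a given size. That size is 1.7 log10, and the claim covers every Arm B cohort of six participants.

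Other sections of the same version report what happened in Arm B:

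- Section 2.2, on the 10 mg/kg cohort: "Cohort 7 never opened to enrollment". It adds that Cohort 8 took no further participants under Protocol Version 4.0.
- Section 4.2.2 gives "limited sample size in Cohort 8 (n=2" as one reason for dropping the viral decay model.
- Section 6.1 says that Cohort 5 "will be closed (although it did not enroll 6 participants". It counts four participants on study during the COVID-19 pause and one already off study.

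For the primary efficacy outcome, Section 4.2.1 specifies a paired t-test with a two-sided 95% confidence interval for the combined Arm B cohort, "and a Wilcoxon signed rank test for each cohort separately", and a Wilcoxon sensitivity test for the combined cohort. Section 1.2 says that Version 4.0 responds to the study closing with Cohort 7 unopened and Cohorts 5 and 8 small. It lists changes to the PK analyses and to some secondary efficacy analyses.

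**The concern.** Version 4.0 exists because Arm B under-enrolled, and it acts on that elsewhere: the Arm A versus Arm B PK regression is declared not feasible and the viral decay model is dropped. The primary efficacy outcome depends on the same few participants, but its size and power statement stays in the present tense, is not marked as planned, and is not reconciled with enrolment. The per-cohort tests also remain.

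The risk is one of interpretation. A non-significant result in Cohort 5 or Cohort 8 could be read as failing to find a drop that the study had 80% power to detect, when the planned test could not have been significant at those sizes at the usual two-sided level.

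**Working it through.** **Inputs**

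- Planned total 53-65, active 39-51, placebo 14; 80% power for a 1.7 log10 drop at N = 6 (SAP 2.5).
- Allocation 2:1 active to placebo in Arms A and C; Arm B all active (SAP 2.2).
- Cohort 7: 0 (SAP 2.2). Cohort 8: 2 (SAP 4.2.2). Cohort 5: fewer than 6 is explicit; 4 + 1 = 5 is inferred (SAP 6.1).
- Alpha is not stated for the power figure or the per-cohort tests. Two-sided 0.05 is assumed, from the two-sided 95% interval in SAP 4.2.1.
- The SD of the change in HIV-1 RNA is not given in the documents.

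**Step 1: the planned total.** Fourteen placebo at 2:1 implies 2 × 14 = 28 active in Arms A and C, so 28 + 14 = 42 there. Arm B is then planned at 39 − 28 = 11 to 51 − 28 = 23. Check: 42 + 11 = 53 and 42 + 23 = 65. The plan's figures are reproduced and add up.

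**Step 2: the total at the reported enrolment.** Arm B: 5 + 0 + 2 = 7, which is 4 below the minimum of 11. If Arms A and C filled as planned, active = 28 + 7 = 35 (stated minimum 39) and total = 42 + 7 = 49 (stated minimum 53).

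**Step 3: the 80% at N = 6.** Without an SD this can be neither confirmed nor refuted. Solving for the SD that gives 80% at N = 6 for a 1.7 log10 drop, two-sided 0.05:

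- Paired t-test (noncentral t): standardised effect 1.4345, so SD = 1.7 / 1.4345 = 1.19.
- Exact Wilcoxon: at N = 6 the test rejects only if all six changes have the same sign. For a normal change with standardised effect d, power is therefore about Φ(d)^6. Setting this to 0.80 gives d = 1.793 and SD = 1.7 / 1.793 = 0.95.

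**Step 4: what the planned per-cohort test can reach.** The smallest exact two-sided Wilcoxon signed rank p-value, with all changes in one direction, is 2 / 2^n. The one-sided value is 1 / 2^n.

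| n | Two-sided minimum p | One-sided minimum p |
|---|---|---|
| 2 (Cohort 8) | 0.50 | 0.25 |
| 5 (Cohort 5, inferred) | 0.0625 | 0.031 |
| 6 (planned cohort) | 0.031 | 0.016 |
| 7 (combined, implied) | 0.016 | 0.008 |

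Six is the smallest cohort that can reach two-sided 0.05. At five and at two, power at that level is 0% for any effect and any SD.

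**Step 5: the same question under a paired t-test, for scale only.** This is not the planned per-cohort test, and the SDs are the two solved for in Step 3. Two-sided 0.05, true drop 1.7 log10:

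| n | SD 1.19 | SD 0.95 |
|---|---|---|
| 2 | 13% | 16% |
| 5 | 67% | 84% |
| 7 combined, same mean drop in both cohorts | 88% | 97% |

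**The case against.** The strongest reply is that Section 2.5 is design text. Its title announces sample size considerations, it speaks of proposed sizes, and a range such as 53-65 can only be a plan. The power sentence is conditional on N = 6 and claims nothing for five or two. The shortfall is disclosed in several other sections, and the report must give the numbers enrolled (5.1) and the size of the efficacy population (5.3).

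Much of this stands. The figures are legitimate as planned values, the sums are right, and nothing shows the 80% to be wrong at N = 6. The reply softens the point but does not remove it. No Arm B cohort meets the condition, Section 2.5 does not report the achieved size, and a version written because of the shortfall adapted the PK and decay analyses but not the per-cohort primary efficacy tests.

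Three stronger readings are tempting, and the documents do not support them:

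- **That Arm B as a whole can only be used for estimation.** The combined analysis is a planned primary efficacy analysis. At n = 7 its Wilcoxon sensitivity test can reach 0.016, and its paired t-test has no such floor.
- **That Section 2.5 contains an arithmetic error.** It does not; the figures are unreconciled with enrolment.
- **That power fell to a known value such as 67% at n = 5.** That figure rests on one solved-for SD and on a test not planned per cohort. The other SD gives 84%.

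**Conclusion.** The point holds as a failure to reconcile Section 2.5 and the per-cohort tests in 4.2.1 with the enrolment that the same SAP reports. Arm B has an implied 7 participants against a planned minimum of 11, and neither enrolled cohort can reach two-sided 0.05 on its planned exact test.

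The conclusion rests on these assumptions:

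- **Cohort 5 has five participants.** The SAP prints no total, but it does say fewer than six, and any size below six leaves the exact two-sided test unable to reach 0.05.
- **Alpha is two-sided 0.05.** At one-sided 0.05, n = 5 could reach 0.031; n = 2 could not (minimum 0.25).
- **The test is exact.** The SAP does not say so.
- **The 49 and 35 depend on Arms A and C having filled as planned.** The SAP does not report Arm C enrolment.
- **All seven enter the efficacy analysis.** Section 4.1.1 also requires entry HIV-1 RNA of at least 5000 copies/mL, so analysable numbers may be smaller, including in the combined analysis.

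**What to change.** - **Section 2.5:** label the 53-65 total and the 80% power as the original design. Add the actual numbers for each Arm B cohort and the actual total and active counts. State that the 80% does not apply to the enrolled cohorts.
- **Section 4.2.1:** state that the per-cohort Day 7 results are descriptive, because the per-cohort Wilcoxon tests cannot reach two-sided 0.05 at the enrolled sizes, and that inference for the primary efficacy outcome rests on the combined Arm B analysis. Give the alpha and sidedness, and say that Wilcoxon p-values are exact.
- **Do not** write that Arm B as a whole is for estimation only.

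The cost is wording; no new data or analysis is needed. The downside is that the stated size and power become less favourable.

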2.6 Overview of Formal Interim Monitoring

The study will undergo SMC review approximately every 6 months, with the first review scheduled no more than 6 months after the enrollment of the first participant. In addition, after the data are available from Day 14 follow-up for the last enrolled participant in each of Cohorts 1-3 and 10, and the sixth enrolled participant in Cohort 4, if there is any Grade 3 or higher AE that is at least possibly

related to study treatment, all safety data, including the decision on the relationships between AEs and study treatment, will be reviewed to determine whether to dose escalate (for Cohorts 1-3 and 10) or continue with multiple infusions (Cohort 4); otherwise a summary letter on safety data will be sent by the study chair to the SMC and dose escalation (Cohorts 1-3 and 10) or multiple infusions (Cohort 4) will proceed without pause. Although the suggested dose escalation (or continuation of multiple infusion) criteria are based on Day 14 safety outcomes for all participants in the previous cohort (or the first six participants in Cohort 4), all available safety information from both arms at the same dose level will be provided in the SMC report and the summary letter to the SMC for a complete review.

If at any time within a given dose cohort in any arm

- a. Three or more participants experience a Grade 3 AE that is probably or possibly related to study treatment (as judged by the CST, blinded to active/placebo treatment), or
- b. Two or more participants experience a Grade 3 AE that is probably related to study treatment (as judged by the CST, blinded to active/placebo treatment), or
- c. One or more participants experience a Grade ≥ 3 AE that is definitely related to study treatment or that is Grade ≥ 4 that is probably or possibly related to study treatment (as judged by the CST, blinded to active/placebo treatment) or
- d. One or more participants experience an SAE that is possibly, probably, or definitely related to study treatment (as judged by the CST, blinded to active/placebo treatment),

Enrollment into the study will be temporarily suspended, subsequent infusions (Cohort 4 only) will be put on hold, and the SMC, unblinded to active/placebo treatment, will be asked to review all safety data; review the relation to study treatment of the event(s) thought by the blinded CST to be a primary safety outcome; and recommend how the study should proceed with respect to resuming enrollment, continuing study treatment, and dose escalation.

For Arm B, after the data are available from Day 14 follow-up for the last enrolled participant in each of Cohorts 5-8, efficacy data will be reviewed by the CST (see Protocol Section 10.4.2) to determine whether to dose de-escalate. This is described in more detail below.

